1. GLOSSARY OF ABBREVIATIONS

Abbreviation	Description
ACS	acute chest syndrome
AE	adverse event
ALT	alanine aminotransferase
AST	aspartate aminotransferase
ATC	Anatomical Therapeutic Chemical
BLQ	below the limit of quantification
BMI	body mass index
CRF	case report form
CTCAE	Common Terminology Criteria for Adverse Events
GBT	Global Blood Therapeutics
Hb	hemoglobin
HbS β^0 thal	sickle hemoglobin (S) and one beta thalassemia gene (β^0 thal)
HbSS	sickle hemoglobin with two sickle cell genes (SS)
HU	hydroxyurea
LDH	lactate dehydrogenase
MedDRA	Medical Dictionary for Regulatory Activities
n	number of participants
NCI	National Cancer Institute
OLE	open-label extension
PK	pharmacokinetic
PT	Preferred Term
RBC	red blood cells
SAE	serious adverse event
SAP	statistical analysis plan
SCD	sickle cell disease
SD	standard deviation
SI	International System of Units
SOC	System Organ Class
TEAE	treatment-emergent adverse event
WBC	white blood cell
WHO	World Health Organization

2. INTRODUCTION

The purpose of this statistical analysis plan (SAP) is to describe the planned analyses of data from Study GBT440-038 (C5341023).

Where applicable, the statistical analysis methods presented in this document will supersede the statistical analysis methods described in the study protocol.

2.1 Study Overview

This multicenter, nonrandomized, global open-label extension (OLE) study is designed to assess the safety of, and sickle cell disease (SCD)-related complications with, long-term treatment with voxelotor in pediatric participants with SCD. The study will be conducted globally and will be available to eligible participants from Global Blood Therapeutics (GBT)/Pfizer-sponsored voxelotor clinical studies. Participants must have completed participation in their originating clinical study and must meet the entry criteria for this study to be eligible for enrollment.

2.2 Study Measurement and Visit Schedule

Please refer to the study protocol, Appendix A and Appendix B, for the schedule of assessments.

3. STUDY OBJECTIVES

The objective of this OLE is to assess the safety of, and SCD-related complications with, long-term treatment with voxelotor in participants who have completed treatment in a GBT/Pfizer-sponsored voxelotor clinical study, based on the following parameters:

- Adverse events (AEs), clinical laboratory tests, physical examinations, and other clinical measures
- Frequency of SCD-related complications

In addition, this study will assess predose whole blood and plasma concentrations of voxelotor, in a subset of participants receiving a modified dose of voxelotor as dispersible tablets at selected sites.

4. STUDY ENDPOINTS

Safety:

• Treatment-emergent adverse events (TEAEs) and serious adverse events (SAEs)

Sickle Cell Disease-Related Complications:

• Frequency of SCD-related complications

5. DEFINITIONS AND TERMINOLOGY

Study Day

Study Day is defined relative to initiation of treatment, i.e., Day 1. Thus, the study day of an event is calculated as:

$$Study Day = event date - Day 1 date + 1.$$

Study Visit

Study Visit is the nominal visit as recorded on the Case Report Form (CRF).

Change from Day 1

Change from Day 1 to follow-up visit will be calculated as Day 1 subtracted from the follow-up measurement for all assessments. Percent change from Day 1 values to post-Day 1 values will be calculated using the following formula where applicable:

Exposure to Study Drug

Duration of exposure to study drug is defined as the number of weeks from Day 1 to the last date of dosing of study drug. The derivation is as follows:

(Last dose date - First dose date
$$+ 1$$
)/7

Actual exposure to study drug is defined as the number of weeks from Day 1 to the last date of dosing of study drug which excludes days where treatment was entirely missed or intermittently stopped as recorded in the CRF. The derivation is as follows:

(Last dose date - First dose date - Number of days study drug was not taken +1)/7

Concomitant Medications

Concomitant medications are those medications taken on or after the initiation of study drug. This definition includes medications started prior to the initiation of study drug, but continuing concurrently with study drug.

Red blood cell (RBC) transfusions are collected on a separate CRF.

Treatment-Emergent Adverse Event

A TEAE is defined as an AE that emerges on or after initiation of study drug (having been absent pre-treatment), or an AE that existed pre-treatment and worsened on treatment (relative to the pre-treatment state) through 28 days after study drug discontinuation. AEs occurring on Day 1 are assumed to be treatment-emergent.

6. GENERAL STATISTICAL CONSIDERATIONS

6.1 Sample Size Considerations

The total sample size for this study will not exceed total enrollment in the originating GBT/Pfizer-sponsored voxelotor clinical studies.

In addition, the collection of voxelotor predose whole blood and plasma concentrations in participants receiving a modified dose of voxelotor dispersible tablets will be conducted in approximately 20 participants at selected sites.

6.2 Handling of Missing or Partial Dates

6.2.1 Missing Start Dates for Concomitant Medication

For missing start day only: day will be imputed as the first day of the month (i.e., 1) with the following exception: If the partial date falls in the same month and year as the treatment start date then the concomitant medication start date will be imputed as the treatment start date.

For missing start day and month: day and month will be imputed as the first day of the year (i.e., 1 January) with the following exception: If the partial date falls in the same year as the treatment start date then the concomitant medication start date will be imputed as the treatment start date.

6.2.2 Missing Start Dates for Adverse Events

For missing start day only: day will be imputed as the first day of the month (i.e., 1) with the following exception: If the partial date falls in the same month and year as the treatment start date then the adverse event start date will be imputed as the treatment start date.

6.3 Analysis Timing

The final study analysis will be based on complete data from the study and performed after all enrolled participants have completed the study or discontinued early (i.e., last participant's last visit has occurred), and all corresponding data have been entered into the database, reviewed, and verified and the database is locked.

Prior to the final study analysis, interim data from this open-label extension study may be summarized as necessary (e.g., interim safety data summarized to support regulatory applications or health authority requests). The data included for the interim analyses will depend on the purpose. If performed, the interim analyses will be descriptive and no formal hypothesis testing performed.

7. ANALYSIS POPULATIONS

7.1 Safety Population

The Safety Population is defined as all participants who receive at least one dose of study drug.

7.2 Pharmacokinetic Population

The pharmacokinetic (PK) population is defined as all participants who take at least 1 dose of voxelotor and in whom at least 1 concentration value is reported.

8. STATISTICAL METHODS

Statistical analyses will be performed using SAS® Version 9.4 or higher.

Continuous variables will be descriptively summarized using number of participants (n), mean, standard deviation (SD), median, minimum, and maximum. Categorical variables will be descriptively summarized by presenting the number (frequency) and percentage in each category. All statistical analyses conducted will be descriptive and no formal statistical tests are planned.

Additionally, for the subset of participants receiving the modified dose of voxelotor in dispersible tablet in this study, separate summaries will be provided for selected CRF data (e.g., TEAEs).

8.1 Participant Disposition, Demographic and Baseline Characteristics

8.1.1 Participant Disposition

The number of participants enrolled will be tabulated by originating study and prior treatment group, country, and study site. Participant disposition will be presented in terms of the numbers and percentages of participants who completed the study including reasons for study termination.

8.1.2 Demographic and Baseline Characteristics

The demographic variables collected in this study include age (years) at Day 1, sex, race, and ethnicity and will be summarized descriptively. Height (cm), weight (kg) and body mass index (BMI; kg/m²) at Day 1 will be presented using descriptive statistics. Participants who record more than one race will be grouped into a single category denoted as multi-racial.

Additional summaries include the number and percentage of participants who currently use hydroxyurea (HU), and who have each SCD genotype (homozygous hemoglobin SS [HbSS] or hemoglobin S beta⁰ thalassemia [HbS β^0 thal]).

Medical history excluding sickle cell history will be summarized by System Organ Class (SOC) and Preferred Term (PT) according to Medical Dictionary for Regulatory Activities (MedDRA), coding dictionary (current version).

8.2 Safety

8.2.1 Summary of Exposure

The duration of study drug exposure and actual study drug exposure will be summarized with descriptive statistics.

The number and percentage of participants who permanently discontinued study drug, and the reason for discontinuation (AE or other) will be summarized as collected on the study drug administration CRF. The number and percentage of participants who missed at least 1 dose of study drug or had at least 1 dose reduction will be summarized. The summary will include the number and percentage of participants who had a dose reduction or dose missed due to an adverse event or other reason. Additionally, the number and percentage of participants will be summarized in categories of number of missed doses and number of dose reductions.

8.2.2 Adverse Events

All AEs will be coded using MedDRA (current version). Adverse events reported for participants participating in this study will be graded using the National Cancer Institute's (NCI) Common Terminology Criteria for Adverse Events (CTCAE), version 5.0. For AEs not adequately addressed in the NCI CTCAE, version 5.0, protocol-specified criteria will be used.

All adverse events summaries described below will be presented for both non-SCD and SCD-related TEAEs.

Non-SCD-related TEAE summary tables will exclude SCD related events including but not limited to the preferred terms of: sickle cell anemia with crisis, acute chest syndrome (ACS), pneumonia, priapism, splenic sequestration, hepatic sequestration, stroke, leg ulcers, dactylitis, and osteonecrosis. Additional TEAE tables will summarize the aforementioned SCD related events.

Overall summaries will be presented which include the number of TEAEs and the number and percentage of participants who experienced at least one TEAE. The summaries will also include TEAEs Grade 3 or greater, TEAE related to study drug, TEAEs leading to study drug reduction, TEAEs leading to study drug interruption, TEAEs leading to discontinuation of study drug, and SAEs. TEAEs leading to deaths will be summarized together regardless if they are SCD-related, as cause of death may include multiple TEAEs.

Additional summaries of TEAEs will be provided showing the number and percentage of participants who experienced at least one TEAE. These summaries will be presented by MedDRA System Organ Class (SOC), Preferred Term (PT) and maximum severity. If a participant reports the same PT multiple times within the same SOC, that PT will only be counted once within that SOC for that participant. As with the PT, if a participant reports multiple conditions within the same SOC, that SOC will only be counted once for that participant.

The occurrence of TEAEs assessed as related to voxelotor by the investigator will be tabulated by SOC, PT, and maximum severity. Serious adverse events will be presented by SOC, PT, and maximum severity.

Grouped terms for rash and abdominal pain will be summarized.

Adverse events recorded in the CRF which began prior to first dose of study drug will not be included in the summary tables.

For the subset of participants receiving a modified dose of voxelotor as dispersible tablets in this study, AEs will be presented with participants grouped by the dosing form prior to the switch to the modified dose.

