8.4. Analysis of Safety

8.4.1. Adverse Events

Adverse events will be classified using the Medical Dictionary for Regulatory Activities (MedDRA). A TEAE is defined as an AE that emerges on or after initiation of study drug (having been absent pretreatment), or an AE that existed pretreatment and worsened on treatment (relative to the pretreatment state). The incidence of TEAEs will be tabulated by system-organ-class (SOC), Preferred Term, severity, and relationship to study drug (as assessed by the investigator).

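### SAP 8.2.2 splits every adverse-event summary by SCD-relatedness except deaths, so the share of participants with any TEAE, any SAE, any Grade 3 or higher TEAE or any related TEAE is not a planned output

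*SAP*

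**What the plan says.** SAP section 4 sets two endpoints: TEAEs and SAEs as the safety endpoint, without qualification, and separately "Frequency of SCD-related complications". Protocol 8.4.1 likewise has no split: "The incidence of TEAEs will be tabulated by system-organ-class (SOC), Preferred Term, severity, and relationship to study drug". SAP section 2 gives the SAP's methods precedence over the protocol's, so SAP 8.2.2 governs.

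SAP 8.2.2 opens its reporting rules with "All adverse events summaries described below will be presented for both non-SCD and SCD-related TEAEs". The two parts do not share events: "Non-SCD-related TEAE summary tables will exclude SCD related events including but not limited to the preferred terms of" a list of named terms, and "Additional TEAE tables will summarize the aforementioned SCD related events". Every summary follows that rule:

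- The overview: "Overall summaries will be presented which include the number of TEAEs and the number and percentage of participants who experienced at least one TEAE". It also covers Grade 3 or greater, related, leading to reduction, interruption or discontinuation, and SAEs.
- The tables by SOC, preferred term and maximum severity, for all TEAEs, for related TEAEs and for SAEs.

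The only stated departure is that "TEAEs leading to deaths will be summarized together regardless if they are SCD-related".

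SAP 8.2.1, which comes before the split rule, plans participant counts from the study drug administration CRF for permanent discontinuation (AE or other reason) and for dose reductions and missed doses due to an AE or other reason. These are not split by SCD-relatedness.

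**The concern.** The endpoint asks how many participants had a TEAE or an SAE. The plan answers for two subsets of events and does not say that it will answer for the whole. The subsets separate events, not participants: someone with a crisis and a rash counts once in each part.

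Both parts are likely to matter. Protocol 1.4 reports that SCD-related TEAEs were common in the Phase 3 study, and that across the SCD studies SAEs were mainly sickle cell crises. The non-SCD table alone could then show far fewer participants with an SAE than the study had, and the two tables together still leave the total open. At stake is whether a long-term safety study of up to about 600 participants reports the headline figures for its own safety endpoint.

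**Working it through.** The plan states no figure on this point, so there is nothing to reproduce. The question is which totals the two planned tables determine.

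**Step 1: what adds.** Each event is in exactly one part, so the total number of TEAEs is the sum of the two event counts. If events are classified by preferred term, each term sits in one part only, and its participant count can be read off directly.

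**Step 2: what does not add.** Let *a* be the share of participants with at least one non-SCD event of a given kind, *b* the share with at least one SCD-related event of that kind, and *c* the share with both. The overall share is

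*p* = *a* + *b* − *c*.

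Neither table reports *c*, so all that is known is

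max(*a*, *b*) ≤ *p* ≤ min(1, *a* + *b*).

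A small example shows that the tables do not fix the total. With 8 participants in each part, full overlap gives 8 + 8 − 8 = 8 overall, and no overlap gives 8 + 8 − 0 = 16. The two printed tables are the same in both cases.

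This applies to any TEAE, any SAE, any Grade 3 or higher TEAE and any related TEAE. It also applies to a SOC with terms in both parts, because SAP 8.2.2 counts each SOC once per participant, and to a participant's maximum severity across both parts.

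**Step 3: how wide the interval can be.** The documents give no adverse-event rates for this study. The rates below are assumptions for illustration. The 600 is the approximate maximum enrolment in Protocol 3.1.

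| Category | Non-SCD *a* (assumed) | SCD *b* (assumed) | Overall, lowest to highest | Participants of 600 |
|---|---|---|---|---|
| Any TEAE | 60% | 70% | 70% to 100% | 420 to 600 |
| Any TEAE | 85% | 75% | 85% to 100% | 510 to 600 |
| Any SAE | 15% | 40% | 40% to 55% | 240 to 330 |
| Any SAE | 10% | 30% | 30% to 40% | 180 to 240 |
| Grade 3 or higher | 20% | 40% | 40% to 60% | 240 to 360 |
| Related TEAE | 20% | 2% | 20% to 22% | 120 to 132 |

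For the first SAE row, the lower bound is max(0.15, 0.40) = 0.40 and the upper bound is 0.15 + 0.40 = 0.55. Assuming independence would give 1 − 0.85 × 0.60 = 0.49, but nothing in the documents supports independence within a participant.

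The width equals the smaller of the two shares until the sum reaches 100%. It is therefore material where both parts are well filled (any TEAE, SAEs, Grade 3 or higher). It is small where one part is nearly empty. Related TEAEs may be such a case, because Protocol 7.2.4 allows common SCD complications to be regarded as unrelated unless they have worsened or changed in nature.

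**The case against.** **The overall summaries may be meant as combined.** Read alone, the word overall suggests this. But the overview follows the rule that all the summaries are given for both parts, and the special sentence on deaths is needed only if the rest is split. At best the text is ambiguous about a declared endpoint, which one sentence would settle.

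**The split is a reasoned choice.** This stands. SCD complications are an endpoint in their own right, Protocol 1.4 already describes Phase 3 safety in these two groups, and a pooled figure would be strongly influenced by the background disease. That is a reason to keep the split tables. It is not a reason to omit the total, and both can be shown.

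**Much of the total is available elsewhere.** This stands in part. A reader might infer that the share of participants stopping, reducing or missing drug because of an adverse event is also lost. It is not: SAP 8.2.1 plans those counts without the split. They come from the study drug administration CRF, so they may not match AE-form counts exactly, but they are participant-level and combined. Deaths are combined too.

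**The boundary between the parts might seem open to manipulation.** A reader might infer this from the open-ended wording, or from dactylitis being named in the SAP but not in the protocol's lists. The documents do not support it. The ten named terms are the same in SAP 8.2.2 and 8.2.3, the protocol's lists are themselves non-exhaustive, and a single-arm, open-label, descriptive study has no comparison to tilt. Pneumonia and stroke are on the protocol's own SCD list and are still reported, in the SCD tables.

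**Conclusion.** The point holds in a limited form. SAP 8.2.2 as written does not plan the participant-level incidence of any TEAE, any SAE, any Grade 3 or higher TEAE or any related TEAE. Nor does it plan combined SOC-level and maximum-severity counts for participants who fall in both parts. None of these can be derived from the two sets of tables. The endpoint in SAP section 4 and the tabulation in Protocol 8.4.1 are not restricted in this way.

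The resulting uncertainty depends on rates that the documents do not give. Under the assumed rates it ranges from 2 percentage points (related TEAEs) to 30 (any TEAE), and is 10 to 15 points for SAEs. The conclusion rests on reading the split rule as covering the overall summaries, which the deaths exception supports.

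It would go too far to say that the trial cannot report its safety endpoint or that information is lost. SAP 8.2.3 has SCD complications recorded as adverse events, so the combined figures can be produced from the same dataset. They are simply not planned. This is an inexpensive improvement to the outputs, not a flaw in the design.

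**What to change.** In SAP 8.2.2:

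1. Add combined rows or a column (SCD-related plus non-SCD-related) to the overall TEAE summary, giving the number and percentage of participants with any TEAE, any Grade 3 or greater TEAE, any related TEAE and any SAE. The rows for reduction, interruption and discontinuation can carry the same column.
2. Add a combined participant total and combined SOC-level counts to the SAE table.
3. Keep the split tables as planned. Combined preferred-term rows are unnecessary, because they would repeat what the split tables show.

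One sentence would do it, for example: *The overall summary will also present each category for all TEAEs combined, and the SAE table will include a combined total and SOC-level count, each participant being counted once.*

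The cost is a SAP wording change and a little extra programming on data already coded, with no new data collection. SOC-level and maximum-severity counts for TEAEs other than SAEs would remain split, which is acceptable once the headline totals are given.

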6.4. Medical History

Ongoing AEs and ongoing concomitant medications from the antecedent studies will be recorded as medical history and concomitant medications, respectively, in this study.

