7.1. Adverse Events

7.1.1. Definition of Adverse Events

An AE is defined as any untoward medical occurrence associated with the use of a drug in humans, whether or not considered to be drug related. An AE can therefore be any unfavorable and unintended sign, symptom, or disease temporally associated with the use of an investigational product, whether or not thought to be related to the investigational product. An AE may also constitute complications occurring as a result of protocol-mandated interventions (eg, invasive procedures such as biopsies), including the period prior to receiving the first dose of the study drug (eg, medication washout). In addition to new events, any increase in the severity or frequency of a preexisting condition that occurs after the participant signs the ICF is considered to be an AE. This includes any side effect, injury, toxicity, or sensitivity reaction.

A suspected adverse reaction is any AE for which there is a reasonable possibility that the drug caused the AE. For the purposes of expedited safety reporting, "reasonable possibility" means there is evidence to suggest a causal relationship between the drug and the AE. Suspected adverse reaction implies a lesser degree of certainty about causality than adverse reaction, which means any AE caused by a drug.

Life-threatening AE or life-threatening suspected adverse reaction is an AE or suspected adverse reaction that, in the view of either the investigator or sponsor, places the study participant at immediate risk of death. It does not include an AE or suspected adverse reaction that, had it occurred in a more severe form, might have caused death.

An AE or suspected adverse reaction is considered to be "unexpected" if it is not listed in the Reference Safety Information (RSI) section of the current IB or is not listed at the specificity or severity that has been observed.

An SAE or serious suspected adverse reaction is an AE or suspected adverse reaction that, at any dose, in the view of the either the investigator or sponsor, results in any of the following outcomes:

- Death
- A life-threatening AE
- Inpatient hospitalization or prolongation of existing hospitalization
- Persistent or significant incapacity or disability (substantial disruption of the ability to conduct normal life functions)
- A congenital anomaly/birth defect

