8.2.3 Frequency of Sickle Cell Disease–Related Complications

SCD-related complications over the course of the treatment period will be recorded as adverse events for each participant. SCD-related complications may include the following: sickle cell anemia with crisis, ACS, pneumonia, priapism, splenic sequestration, hepatic sequestration, stroke, leg ulcers, dactylitis, and osteonecrosis. SCD-related complications will be summarized in the SCD-related adverse event summaries as described in Section 8.2.2.

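### Read literally, SAP 8.2.2 keeps out of the tables a pre-dose AE that worsened on treatment, which SAP 5 counts as a TEAE

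*SAP*

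**What the plan says.** The TEAE definition has two limbs. The first covers AEs that emerge once study drug has started. The second, in SAP Section 5, covers "an AE that existed pre-treatment and worsened on treatment (relative to the pre-treatment state) through 28 days after study drug discontinuation". Protocol Section 8.4.1 has the same second limb. SAP Section 5 adds that AEs occurring on Day 1 are assumed to be treatment-emergent.

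SAP Section 8.2.2 describes the AE tables as summaries of TEAEs, split into non-SCD-related and SCD-related events. It then adds: "Adverse events recorded in the CRF which began prior to first dose of study drug will not be included in the summary tables". No exception is written.

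The second endpoint uses the same tables. SAP Section 8.2.3 says: "SCD-related complications will be summarized in the SCD-related adverse event summaries as described in Section 8.2.2".

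Three protocol rules decide which pre-dose AEs can be on the AE CRF at all:

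- Section 6.9 starts AE recording at consent or assent, not at first dose.
- Section 6.4 sends carried-over events elsewhere: "Ongoing AEs and ongoing concomitant medications from the antecedent studies will be recorded as medical history and concomitant medications, respectively".
- Section 7.1.1 provides that "any increase in the severity or frequency of a preexisting condition that occurs after the participant signs the ICF is considered to be an AE".

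**The concern.** An AE that existed before treatment must have begun before first dose. If its CRF record keeps that start date, the exclusion in SAP 8.2.2 cancels the second limb of the SAP's own definition. Two programmers could each follow the SAP faithfully and count the same record differently.

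TEAEs and SAEs are the safety endpoint and SCD-related complications are the only other one, so this sentence governs the reporting of both. Any loss would run in one direction. The records at risk are those that became worse on treatment, so they could also be missing from the rows for Grade 3 or greater and from the tables by maximum severity. No hypothesis test is involved, because all analyses are descriptive.

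**Working it through.** The plan gives no figure on this point, so the check is mainly one of wording, with two short pieces of arithmetic.

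**Timing by date.** SAP Section 5 defines Study Day = event date − Day 1 date + 1.

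- Onset one day before first dose: −1 + 1 = Study Day 0.
- Onset on the dosing date: 0 + 1 = Study Day 1.

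At date level, only records with Study Day 0 or earlier can meet the exclusion. SAP Section 6.2.2 also works by date: an AE with a missing start day in the month and year of treatment start is given the treatment start date, so it stays in.

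**Each type of record under both SAP rules.**

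| Record | SAP 5 | SAP 8.2.2, read literally | Agree? |
|---|---|---|---|
| 1. Onset after first dose | TEAE | Kept | Yes |
| 2. Onset on a date before first dose, did not worsen | Not a TEAE | Dropped | Yes |
| 3. Onset on a date before first dose, worsened on treatment, one record with the original start date | TEAE | Dropped | **No** |
| 4. Onset on Day 1, before the dose | TEAE by the Day 1 assumption | Not stated whether the date or the clock time decides | Ambiguous; resolved at date level by SAP 5 |
| 5. Antecedent-study AE held as medical history, worsens after first dose | TEAE | Kept if entered as an AE dated at the worsening; dropped if entered with its original date | Depends on the recording convention |

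The contradiction is row 3. Row 5 joins it only if sites enter the original date.

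**Which convention applies.** Protocol Section 7.2.3 implies a fresh entry when severity, seriousness or etiology changes, but only for laboratory abnormalities. For other AEs, Section 7.2.1 asks for severity, relationship, duration and outcome as a minimum and does not name a date of worsening. Section 11.7 refers to a separate CRF Completion Requirement document, which may settle the matter; it is not among the documents reviewed.

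**How many records could be affected.** Appendix A schedules consent on Day 1, and Protocol Section 6 regards enrollment on the day of the antecedent study's last visit as optimal. If consent and first dose share a date, no AE arising after consent can have Study Day 0 or earlier, and row 3 is empty. Row 3 needs an interval of at least one calendar day between consent and first dose.

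**Scale.** The number of affected participants is not in the documents. At the planned ceiling of about 600 participants, each one whose only record of a term is excluded lowers that term's incidence by 1/600 = 0.17 percentage points. With a smaller safety population of N, the step is 100/N points. If every worsening has its own record with its own onset date, the effect is zero.

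**The case against.** The strongest reply is that the sentence means only that events that are not treatment-emergent stay out of the tables. Section 5 supplies the definitions, and 8.2.2 says its summaries are of TEAEs. On this reading the sentence still does some work, because the line on serious adverse events in 8.2.2 is not itself limited to treatment-emergent ones. This reading is possible, but it is not what the sentence says, and nothing in the SAP ranks Section 5 above 8.2.2.

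The second reply concerns reach, and most of it stands. Under the planned schedule, consent and dosing fall on Day 1. Carried-over AEs are medical history. An increase in severity after consent is itself an AE, and the natural onset date for that AE is the date of worsening. Painful crises and acute chest syndrome are discrete episodes that would normally have their own onset dates, so the effect on the SCD endpoint is likely to be slight. Protocol Section 7.1.1 does provide for AEs before first dose, but in general definitional text whose examples, biopsies and washout, are not in Appendix A. These points shrink the affected set. They do not empty it, because no passage in the protocol or SAP fixes the onset date of a worsened non-laboratory AE.

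Three stronger readings might be inferred, and the documents support none of them:

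- *That TEAEs will in fact be lost.* This depends on a recording convention that the documents do not give.
- *That Day 1 is a second contradiction.* The SAP's timing rules work by date, and the Day 1 assumption in Section 5 resolves the case. What is missing is a cross-reference in 8.2.2.
- *That the SAP overrides the protocol's definition.* SAP Section 2 says that, where applicable, "the statistical analysis methods presented in this document will supersede the statistical analysis methods described in the study protocol". But SAP 5 repeats the protocol's second limb, so the two documents agree on the definition. The conflict lies between two sections of the SAP, which that clause does not address.

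**Conclusion.** The concern holds as a minor inconsistency within the SAP. As worded, the exclusion in 8.2.2 contradicts the worsening limb of the TEAE definition in SAP 5. It could keep a worsened AE with a pre-dose start date out of the tables that report both endpoints.

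Confidence is high on the conflict in wording and low on any effect on counts. The effect is probably very small and may be zero. A loss requires two things together: an AE record with a start date before the date of first dose, whether from a gap between consent and dosing or from a carried-over condition entered with its original date, and a worsening on treatment that is not given its own record or date.

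**What to change.** Replace the sentence in SAP 8.2.2 with:

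> *AEs that began before the date of first dose and did not worsen on treatment are not included in the summary tables; those that worsened on treatment are counted as TEAEs as defined in Section 5, with onset at the date of worsening. AEs with onset on Day 1 are counted as TEAEs, as in Section 5.*

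Then confirm that the CRF completion guidance captures worsening either as a new record or with a date of worsening. If it uses a new record, count that record and not the original one as well.

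The cost is one sentence replaced by two and one check of existing guidance. If worsening is already captured, no new data or tables are needed. If it is not, one site instruction is required.
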